7.0 Local Number of Subjects

7.1 *Indicate the total number of subjects that will be enrolled or records that will be reviewed locally.*

Response: 30 participants, made of 15 patient and family member dyads, will be enrolled. Each one of the participants must have a household family member willing to collaborate in the program.

7.2 *If applicable, indicate how many subjects you expect to screen to reach your target sample (i.e. your screen failure rate).*

Response: We expect to screen approximately 50-75 individual patients in order to recruit 12 patient and family member dyads who complete 75% of their visits.

We are planning to enroll 15 dyads, but anticipate that 3 will not complete 75% of their visits.

7.3 *Justify the feasibility of recruiting the proposed number of eligible subjects within the anticipated recruitment period. For example, how many potential subjects do you have access to? What percentage of those potential subjects do you need to recruit?*

Response: The NAVIGATE program admits 2 to 3 patients per month. At the beginning of the study, we anticipate that there would be approximately 40-45 patients in the program with the requisite use of antipsychotic medications, and over the next five months, we would expect an additional 10-15 patients. Assuming that 50% of the patients are eligible and interested, we would have approximately 25-30 patients available for the study.

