8.0 Inclusion and Exclusion Criteria*

8.1 *Describe the criteria that define who will be **included** in your final study sample.*

NOTE: This may be done in bullet point fashion.

Response:

Participant:

-Age 14-26 years

-Enrolled in NAVIGATE, a clinical program for patients with first episode of psychosis.

-Prescribed antipsychotic medication for a first break psychotic episode

-Availability of household family member to collaborate in the weight management program.

Family Member:

-Lives in the same household as participant (e.g., parent, guardian, grandparent, aunt or uncle)

-Able to attend weekly meetings with a case manager

8.2 *Describe the criteria that define who will be **excluded** from your final study sample.*

NOTE: This may be done in bullet point fashion.

Response:

Participant & Family Member:

-Personal or Family history or evidence of current eating disorders (bulimia or anorexia or binge eating disorder)

- Current alcohol or drug abuse,
- Unable to read at 8th grade level
- Unable to use technology.
- Unable to weigh themselves daily due to existing medical condition
- Pregnant or planning on becoming pregnant during the study

8.3 *Indicate specifically whether you will include any of the following special populations in your study using the checkboxes below.*

NOTE: Members of special populations may not be targeted for enrollment in your study unless you indicate this in your inclusion criteria.

Response:

- Adults unable to consent
- Individuals who are not yet adults (infants, children, teenagers)
- Pregnant women
- Prisoners

8.4 *Indicate whether you will include non-English speaking individuals in your study. Provide justification if you will exclude non-English speaking individuals.*

*In order to meet one of the primary ethical principles of equitable selection of subjects, non-English speaking individuals may **not** be routinely excluded from research as a matter of convenience.*

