Families will receive a 12-week FBT adapted for first episode psychosis. This will be delivered in 12 weekly meetings with a trained case manager and two “eating plan” education sessions. Both the patient with psychosis and parents are targeted for eating and activity/exercise change to ensure a change in the shared family environment, which will also help weight control in both sets of participants, as well as medical issues that accompany obesity, including glycemic control, hypertension and hyperlipidemia. If parents are not overweight/obese, they will still target improved health behaviors. They will learn about GREEN, YELLOW, and RED foods (healthy vs. unhealthy foods), energy density, glycemic index of foods, reducing serving sizes, eating less, healthy lifestyle and programmed activity programs and recording their diets and activity. Weekly sessions will involve discussion of weight loss principles presented in modules in the weight control manual, and coaching parents and patients how to implement the Traffic Light Eating Plan and healthy lifestyle techniques. At each session, participants meet with staff and attend a brief problem solving session with their case manager where they will troubleshoot any expected or encountered issues with implementing the program. As part of treatment, participants will weigh themselves daily with a Bluetooth scale. Contingency management (\$1 per completed weighing) will be used to facilitate adherence to this weighing schedule.

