An innovative aspect of this treatment is helping patients develop alternative reinforcements that do not involve food that can reduce the motivation to eat for the hedonic or reinforcing motivations. The first step is to identify alternative activities that have a higher reinforcement value than the patients’ favorite foods. First, participants will identify potential alternatives from the 139 behaviors on the Pleasant Activities List. The therapist then works with the patient to better specify the behavior, ensure its feasibility and describe the parameters of the behavior (e.g. duration). After the participant and case manager agree on a list of alternatives (at least 5), the participant will complete the Behavioral Choice Questionnaire that assesses the reinforcing value of that activity in comparison to food. The most reinforcing food to be used to assess behavioral substitutes will be chosen from a list of usual meals that can be obtained from home cooked, fast food or casual dining restaurants. These alternative reinforcements are used non-contingently by the patients/parents to provide highly desirable activities that compete with excessive food consumption.

At the end of treatment, the patient and family member will receive the same assessment battery that they completed for the baseline session. They will also provide information on the implementation of the diet, exercise, and alternative reinforcement procedures.

After an additional 2 months, the patient and family member will return for the final assessment using the same assessment battery, as well as the

implementation data. Families will be compensated for completing the assessment, sign their payment form, and be debriefed.

11.2 Describe what data will be collected.

NOTE: For studies with multiple data collection points or long-term follow up, consider the addition of a schedule or table in your response.

Response: The primary data collected will be daily weight, which will be taken with a Bluetooth scale that they will be given by the project. This data will be collected throughout the 2 month baseline, 3 month intervention, and 2 month follow up.

At the beginning of the baseline, and the end of treatment, and at the end of the follow-up patients and parents will complete a questionnaire including the Behavioral Choice Questionnaire, and scales regarding parenting, time perspective, and consideration of future consequences.

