19.0 Provisions to Monitor the Data to Ensure the Safety of Subjects*

- N/A:** This study is not enrolling subjects, or is limited to records review procedures only. This section does not apply.

NOTE: *Minimal risk studies may be required to monitor subject safety if the research procedures include procedures that present unique risks to subjects that require monitoring. Some examples include: exercising to exertion, or instruments that elicit suicidality or substance abuse behavior. In such cases, N/A is not an acceptable response.*

19.1 *Describe the plan to periodically evaluate the data collected regarding both harms and benefits to determine whether subjects remain safe.*

Response: Participants in this study continue with their regular psychiatric appointments along with this additional intervention. Assessing the weight of patients on antipsychotic medications is part of the treatment guidelines for patients on these medications.

19.2 *Describe what data are reviewed, including safety data, untoward events, and efficacy data.*

Response: Weights will be monitored weekly by the case manager.

19.3 *Describe any safety endpoints.*

Response: NA

19.4 *Describe how the safety information will be collected (e.g., with case report forms, at study visits, by telephone calls with participants).*

Response: NA

19.5 *Describe the frequency of safety data collection.*

Response: NA

19.6 *Describe who will review the safety data.*

Response: See section 20.2.

19.7 *Describe the frequency or periodicity of review of cumulative safety data.*

Response: NA

19.8 *Describe the statistical tests for analyzing the safety data to determine whether harm is occurring.*

Response: NA

19.9 *Describe any conditions that trigger an immediate suspension of the research.*

Response: NA

20.0 **Withdrawal of Subjects***

N/A: This study is not enrolling subjects. This section does not apply.

20.1 *Describe anticipated circumstances under which subjects may be withdrawn from the research without their consent.*

Response: Participants who leave the NAVIGATE program or experience a psychotic relapse requiring hospitalization longer than one week will be removed from the study. Parents or support participants of the withdrawn participant may continue the study.

20.2 *Describe any procedures for orderly termination.*

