NOTE: Examples may include return of study drug, exit interview with clinician. Include whether additional follow up is recommended for safety reasons for physical or emotional health.

Response: A final phone call with the participant and/or family member will take place. Arrangements to collect the Bluetooth scale will be made.

20.3 Describe procedures that will be followed when subjects withdraw from the research, including retention of already collected data, and partial withdrawal from procedures with continued data collection, as applicable.

Response: No further treatment or assessments will be conducted on the withdrawn participant. However, any participant that is still willing to participate can continue the study. Data will be maintained for participants who remain in the study through 50% of the weight intervention program. Data for participants who withdraw sooner will also be retained for comparison to those who complete the intervention with respect to response to treatment.

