26.0 Consent Process

26.1 *Indicate whether you will be obtaining consent.*

NOTE: This does not refer to consent documentation, but rather whether you will be obtaining permission from subjects to participate in a research study. Consent documentation is addressed in Section 29.0.

Yes *(If yes, Provide responses to each question in this Section)*

No *(If no, Skip to Section 29.0)*

26.2 *Describe where the consent process will take place. Include steps to maximize subjects' privacy.*

Response: The participant and the family member will be consented separately in a private office in the clinic. The patient will be consented first, and if the patient agrees, the family member will then be consented.

26.3 *Describe how you will ensure that subjects are provided with a sufficient period of time to consider taking part in the research study.*

NOTE: It is always a requirement that a prospective subject is given sufficient time to have their questions answered and consider their participation. See “SOP: Informed Consent Process for Research (HRP-090)” Sections 5.5 and 5.6.

Response: Potential subjects will be offered the opportunity to participate in the trial. If interested, research staff will review the consent form with potential subjects at their convenience. Potential subjects are encouraged to review the consent form and are permitted to take a copy home/keep a copy for review prior to signing. Potential subjects are also encouraged to discuss participation with their primary care doctor or treating psychiatrist.

26.4 Describe any process to ensure ongoing consent, defined as a subject’s willingness to continue participation for the duration of the research study.

Response: Ongoing consent will be assessed at the weekly sessions.

26.5 Indicate whether you will be following “SOP: Informed Consent Process for Research (HRP-090).” Pay particular attention to Sections 5.4-5.9. If not, or if there are any exceptions or additional details to what is covered in the SOP, describe:

- *The role of the individuals listed in the application who are involved in the consent process*
- *The time that will be devoted to the consent discussion*
- *Steps that will be taken to minimize the possibility of coercion or undue influence*
- *Steps that will be taken to ensure the subjects’ understanding*

Response:

We have reviewed and will be following “SOP: Informed Consent Process for Research (HRP-090).”

Non-English Speaking Subjects

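### Section 19 reviews only weight, so the hunger and activity discomfort named in 21.3 cannot be counted; separately, the family-member screen lists no eating-disorder item

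*Combined protocol and SAP*

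**What the plan says.** Section 19.2 asks which data are reviewed, untoward events included. The whole answer is "Weights will be monitored weekly by the case manager". Safety endpoints (19.3), method of collection (19.4), frequency (19.5), cumulative review (19.7) and analysis (19.8) are each answered NA. Section 19.6, on who reviews, points to section 20.2, which in the current numbering deals with the closing phone call and return of the scale. Section 19.1 relies on usual care: "Participants in this study continue with their regular psychiatric appointments along with this additional intervention".

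Section 21.3 names two program effects in advance: hunger from altered eating, and discomfort from altered activity. The instruments listed in 11.3 include no adverse-event or symptom form.

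Other contacts exist. In the weekly sessions dyads "troubleshoot any expected or encountered issues with implementing the program" (11.1), and section 26.4 adds "Ongoing consent will be assessed at the weekly sessions". Both members are taught to record diet and activity. At the end of treatment and at the final assessment, "They will also provide information on the implementation of the diet, exercise, and alternative reinforcement procedures". For patients only, 11.4 draws comorbid conditions, medications, lipids and a glycaemic marker from the chart. After withdrawal, "No further treatment or assessments will be conducted on the withdrawn participant" (20.3).

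On eligibility, 8.2 excludes patients and family members alike for "Personal or Family history or evidence of current eating disorders". Section 10.1 checks the patient's chart for an eating disorder. For the family member it lists household residence, willingness, substance use, technology, daily weighing and pregnancy.

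**The concern.** The primary objective includes acceptability (section 1.0). The two secondary endpoints, session participation and the percentage of daily weights reported, measure adherence. They show who stopped or slackened, but not whether hunger, discomfort or illness was the reason. A pilot of a diet and activity program would normally be expected to say how many people found it hard to tolerate. Here the effects that the protocol itself names have no numerator, in either role.

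Family members are half of those enrolled and are targets of the same eating and activity change. They have no chart review and, apart from weight, no specified measure of harm.

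The screening gap is a separate matter of eligibility. The protocol treats eating disorders as a reason not to take part, for both members. If the family-member call follows 10.1 as written, someone whom 8.2 would exclude could be enrolled.

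**Working it through.** The protocol states no safety figure, so there is none to reproduce. The check sets each possible source against what a count needs, and then asks what a count could show.

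**Does any source give a count over a known denominator?**

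- Weekly troubleshooting and the consent check: both members, 12 sessions, no record of harms specified.
- Diet and activity records: both members; they could hint at over-restriction, but are not described as a record of harms.
- Implementation data: both members, 2 late time points, content unspecified. Anyone withdrawn before them supplies none.
- Chart and psychiatric visits: patients only. Admissions and injuries are not among the fields listed in 11.4.
- Weights: both members, reviewed weekly. Marked restriction might show; hunger and discomfort would not.

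None gives a count for 15 patients or for 15 family members.

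**Who might be missed by the late time points?** Section 7.2 says "We are planning to enroll 15 dyads, but anticipate that 3 will not complete 75% of their visits", which is 3/15 = 20%. Missing visits is not the same as withdrawing, and the number who withdraw is not given; among these dyads it could be 0 to 3.

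**What could a count show?** Inputs: n = 15 per role (section 7.1) and true event rates of 5%, 10% and 20%. The rates are assumptions, because the protocol gives none.

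Probability of at least one event = 1 − (1 − p)^15:

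- p = 5%: 1 − 0.95^15 = 53.7%
- p = 10%: 1 − 0.90^15 = 79.4%
- p = 20%: 1 − 0.80^15 = 96.5%

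Upper limit with zero events among 15: one-sided 95%, 1 − 0.05^(1/15) = 18.1%; two-sided 95%, 1 − 0.025^(1/15) = 21.8%. A single event in 15 has an exact two-sided 95% interval of 0.2% to 31.9%.

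The two roles should be kept apart. Only patients take antipsychotics, and members of a dyad share a household, so 30 people are not 30 independent observations.

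**How many usable contacts are there?** 12 sessions + end-of-treatment assessment + final assessment = 14. The baseline assessment comes before any diet or activity change and is not counted. No research visit falls inside the 60-day follow-up, 60/(60 + 90 + 60) = 29% of study days. Events there would be recalled at the final assessment, although daily weights continue.

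**Is the family-member exclusion applied?** Set side by side, 8.2 covers both members, while 10.1 checks eating disorders for the patient and lists no such item for the family member. The patient's chart might mention family history, but 10.1 describes the chart check as concerning the patient's own disorder.

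**The case against.** The strongest reply is that this is a permissible choice. The note that opens section 19 allows lighter monitoring in minimal-risk research and rules out a not-applicable answer only where procedures carry special risks, such as exercise to exertion. The program is education, coaching and lifestyle activity. That stands: the NA answers do not show that the template was breached or that participants are unsafe, and a reader should not infer either. It does not make a short note costly or contentious.

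Tolerability is also not a listed endpoint. That is true; its link is to the acceptability objective, which is why the gain is called modest.

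The effects that the protocol names are mild, and injury and new eating-disorder symptoms are this review's additions. That also stands. Those two items belong in the note because they cost little once it exists.

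A reader might infer that relapse admissions of one week or less would be lost for good. The documents do not support that. To apply the removal rule in 20.1 the team must learn of admissions and their length, the program director is a co-investigator, and the chart may be opened throughout. For patients, admissions are largely recoverable; they are simply not a listed field.

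A reader might also infer from 19.6 that nobody reviews safety data. More likely the reference to 20.2 is a stale pointer to 19.2, which names the case manager; the section numbers in the table of contents already differ from those in the body.

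Finally, the weight control manual, the project manual and any screening script are not among the documents. They may contain a harms or eating-disorder item. The point is therefore about what the protocol specifies.

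**Conclusion.** The point holds in a limited form. If the plan is followed as written, hunger and activity discomfort go uncounted in both roles, and the eating-disorder exclusion may not be applied to family members. Both are worth correcting because correction is cheap.

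The size is modest. With 15 per role, the result would be a descriptive table able to exclude only rates above about 18% when no event is seen. It could not attribute events to the program.

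It would be tempting to conclude that the trial's main result is weakened, or that most of the study goes unobserved because the two 60-day phases have no research visits between their start and end. Neither follows. No weight, participation or growth-curve quantity depends on section 19. The baseline phase comes before any program exposure, and daily weights run through both phases.

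The conclusion assumes that all 15 dyads are enrolled, that event rates lie in the illustrative 5% to 20% range, and that no unseen manual or form already records these events.

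**What to change.** 1. **Section 10.1:** add one eating-disorder question to the family-member phone screen, matching 8.2.
2. **Sections 19.3 to 19.5:** replace NA with a brief event note for each member of the dyad: hunger or activity discomfort, injury, and any hospitalisation or relapse of any length. Complete it at the 12 weekly sessions, the end-of-treatment and final assessments, and any withdrawal call. Ask about new eating-disorder symptoms privately, and only at those two assessments and the withdrawal call. Add patient admissions to the chart fields in 11.4.
3. **Sections 19.6 and 19.8:** name the reviewer's role directly, and report descriptive counts by role for all enrolled participants, with no test.
4. **Referral:** pass positive eating-disorder or relapse answers to the treating team, or to the family member's own doctor.

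No monthly cumulative review or weekly eating-disorder questioning is needed in a pilot of this risk. Suspension conditions (19.9) remain for the investigators and the IRB.

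Cost: at most 14 × 30 = 420 scheduled notes. At an assumed 2 to 5 minutes each, that is 28 to 70 minutes per person over the study, or 3% to 8% of a one-hour contact (2/60 to 5/60). Add a protocol amendment, presumably with matching consent and assent text, and a way to speak to each member separately when sessions are joint or by video. Private questions to participants as young as 14 may cause some of the discomfort that 21.3 already mentions, which is why they are confined to few contacts. Asking more often during treatment will raise counts in that phase, so the report should say that counts are not comparable across phases.

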21.0 Risks to Subjects*

21.1 List the reasonably foreseeable risks, discomforts, hazards, or inconveniences to the subjects related to their participation in the research. Consider physical, psychological, social, legal, and economic risks. Include a description of the probability, magnitude, duration, and reversibility of the risks.

NOTE: Breach of confidentiality is always a risk for identifiable subject data.

Response: The primary risk to participants is the breach of confidentiality. Participants will be assessed and treated within an existing clinic setting from an experienced therapist. Given the strict maintenance of confidentiality in these clinic settings, this risk is very low.

21.2 Describe procedures performed to lessen the probability or magnitude of risks, including procedures being performed to monitor subjects for safety.

Response: Research staff who collect consent forms and assess the patients will be trained in the ethical treatment of research participants, with a particular focus on some challenging confidentiality issues, particularly if they know the participant. Under these circumstances, another individual will be responsible for collecting information and consenting the participants and their participating family member.

21.3 If applicable, indicate which procedures may have risks to the subjects that are currently unforeseeable.

Response: Participants may feel uncomfortable answering some of the sensitive questions about their health and decisions. Participants may experience hunger

from changes to eating patterns and possible discomfort to changes in physical activity.

21.4 If applicable, indicate which research procedures may have risks to an embryo or fetus should the subject be or become pregnant.

Response: N/A

21.5 If applicable, describe risks to others who are not subjects.

Response: NA

